**Table 7: ARIA-E and ARIA-H Radiographic Severity Scales**

ARIA-E Characterization:	Severity/Grade		
<5 cm monofocal	Mild (Grade 1)		
<5 cm multifocal	Mild+ (Grade 2)		
5-10 cm monofocal	Moderate (Grade 3)		
5-10 cm multifocal	Moderate+ (Grade 4)		
>10 cm monofocal/multifocal	Severe (Grade 5)		
Incident ARIA-H:	Mild	Moderate	Severe
Microhemorrhages	1-4	5-9	10 or more
Areas of leptomeningeal hemosiderosis	NA	1	2 or more
Macrohemorrhages	NA	NA	1 or more

ARIA-E=amyloid-related imaging abnormalities-edema; ARIA-H=amyloid-related imaging abnormalities-hemosiderin deposits; NA=not applicable.

Overall, ARIA-H radiographic severity is defined as the worst individual radiographic severity for microhemorrhages, leptomeningeal hemosiderosis or macrohemorrhages (eg, if there are 4 incident microhemorrhages, 1 incident areas of leptomeningeal hemosiderosis, and no macrohemorrhages, then ARIA-H is rated as “Moderate”).

ARIA-H findings very rarely resolve radiographically; it is more typical for ARIA-H findings to stabilize radiographically. Radiographic stabilization of an ARIA-H finding is defined as when a follow-up MRI scan shows no increase in number/size/extent of previously seen cerebral microhemorrhages, leptomeningeal hemosiderosis, and cerebral macrohemorrhages.

#### **7.11.1. Schedule of MRI Surveillance for ARIA**

Surveillance for treatment-emergent ARIA will be accomplished with MRI scans as described in the Schedule of Assessments (Table 9).

If new or worsening ARIA is observed on any of the MRIs conducted, dosing should be managed as prescribed in the Dosing Guidelines for ARIA (see Table 8).

#### **7.11.2. Participant Follow-up for ARIA Events**

Participants with new or worsening radiographic evidence of ARIA on post-baseline MRI scans should be evaluated for neurological signs or symptoms during an unscheduled visit.

Investigators should comprehensively review the BMW for the presence of ARIA or other abnormalities. When ARIA has been detected, follow-up BMWs should be reviewed for radiographic evolution/resolution/stabilization of findings. Investigators suspecting ARIA that has not been detected by the MRI Central Reader should contact the Medical Monitor. For instance, if a local radiologist detects a faint area of vasogenic edema or microhemorrhage, which was not documented in the BMW, the Investigator should contact the Medical Monitor.

If participants are determined to have ARIA related symptoms or signs, the Medical Monitor should be contacted within 48 hours. An evaluation of neurologic signs or symptoms may be assessed during an unscheduled visit.

Participants with asymptomatic ARIA-E should be observed; for participants with mild or moderate symptomatic ARIA-E, the use of oral or IV steroids may be considered (see [Table 8](#) below). In the case of severe symptomatic ARIA-E, it is recommended to hospitalize the participant for close observation and consider the use of IV steroids such as high-dose dexamethasone or a similar agent.

All new cases of ARIA-E and/or new cases of ARIA-H will require unscheduled MRI scans every 4-6 weeks until ARIA-E has resolved and/or until ARIA-H has stabilized without new findings. In addition, the Sponsor may request that additional unscheduled MRIs be performed for the detection and follow-up of ARIA.

An Amyloid PET scan should be requested after the first occurrence of ARIA-E for those participants who have opted in to have longitudinal Amyloid PET performed. An unscheduled LP for CSF analysis and plasma may be requested, if not contraindicated, after any occurrence of ARIA-E and/or ARIA-H.

Participants with MRI evidence of ARIA at any visit will be managed according to the guidelines in [Table 8](#).

**Table 8: Dosing Guidelines for ARIA**

Finding	Asymptomatic/Symptomatic	Action
Mild a ARIA-E	Asymptomatic or Symptomatic	Suspend dosing until resolution of ARIA-E or stabilization of ARIA-H. After resolution (ARIA-E) and/or stabilization (ARIA-H), if participant dosing is restarted, they must receive the same dose they received immediately prior to the ARIA-E/ARIA-H findings. After resuming dosing, 5-10 days before their second post-resumption dose, participants must undergo an unscheduled MRI that must be assessed by the central reader for ARIA-E/H before the next dose is administered. Participants who are undergoing dose titration when the ARIA occurs may continue up-titrating at the second post-resumption dose.  For mild or moderate symptomatic ARIA-E the use of oral or IV steroids can be considered.  For severe symptomatic ARIA-E it is recommended to hospitalize the participant for close observation and consider the use of IV steroids such as high-dose dexamethasone or a similar agent.
Moderate b ARIA-E	Asymptomatic or Symptomatic	
Severe ARIA-E	Asymptomatic or Symptomatic	
Mild or Moderate ARIA-H	Asymptomatic	
Mild or Moderate ARIA-H	Symptomatic	Permanently discontinue treatment
Severe ARIA-H	Asymptomatic or Symptomatic	Permanently discontinue treatment
Serious c ARIA-E or Serious ARIA-H	Symptomatic	Permanently discontinue treatment

**Table 8: Dosing Guidelines for ARIA (Continued)**

Finding	Asymptomatic/Symptomatic	Action
Serious c ARIA-E or Serious ARIA-H	Asymptomatic	Suspend dosing until resolution of ARIA-E or stabilization of ARIA-H. After resolution (ARIA-E) and/or stabilization (ARIA-H), if participant dosing is restarted, they must receive the same dose they received immediately prior to the ARIA-E/ARIA-H findings. After resuming dosing, 5-10 days before their second post-resumption dose, participants must undergo an unscheduled MRI that must be assessed by the central reader for ARIA-E/H before the next dose is administered. Participants who are undergoing dose titration when the ARIA occurs may continue up-titrating at the second post-resumption dose.
A second occurrence of ARIA-E after full resolution of a prior occurrence of ARIA-E	Asymptomatic or Symptomatic	Permanently discontinue treatment

ARIA=amyloid-related imaging abnormality; ARIA-E=amyloid-related imaging abnormality-edema; ARIA-H=amyloid-related imaging abnormality-hemosiderin deposits; MRI=magnetic resonance imaging.

a Mild includes ‘mild’ and ‘mild+’, as scored on the BMW from the Central Reader.

b Moderate includes ‘moderate-’ and ‘moderate+’, as scored on the BMW from the Central Reader.

c Meets criteria for a SAE.

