## 7.3. Definition of Serious Adverse Events

An SAE is defined as any AE that fulfills one or more of the following criteria:

- Results in death
- Is immediately life-threatening
- Requires inpatient hospitalization or prolongation of existing hospitalization
- Results in persistent or significant disability/incapacity
- Results in congenital anomaly/birth defect
- Is an important medical event that may jeopardize the participant or may require medical intervention to prevent one of the outcomes listed above.

Important medical events that may not meet one of the above criteria could be considered a SAE by the Investigator when, based upon appropriate medical judgment, they are considered clinically significant and may jeopardize the participant, or may require medical or surgical intervention to prevent one of the outcomes listed above.

An AE is considered “life-threatening” if, in the opinion of either the Investigator or the Sponsor, its occurrence places the participant at immediate risk of death. It does not include an AE that, had it occurred in a more severe form, might have caused death.

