**Table 6: Adverse Event Grading Criteria**

Grade	Severity	Description
1	Mild	Asymptomatic or mild symptoms; clinical or diagnostic observations only; intervention not indicated
2	Moderate	Minimal, local, or noninvasive intervention indicated; limiting age-appropriate instrumental ADL a
3	Severe or medically significant but not immediately life-threatening	Hospitalization, or prolongation of hospitalization indicated; disabling, limiting self-care ADL b
4	Life-threatening consequences	Urgent intervention indicated
5	Death	Death related to AE

ADL=activities of daily living, AE=adverse event.

a Instrumental ADL refer to preparing meals, shopping for groceries or clothes, using the telephone, managing money, etc.

b Self-care ADL refer to bathing, dressing and undressing, feeding self, using the toilet, taking medications, and not bedridden.

Note that “severity” is a measure of intensity and that a severe AE is not necessarily an SAE.

Changes in the severity of an AE should be documented to allow assessments of the duration of the events at each level of intensity. AEs characterized as intermittent do not require documentation of onset and end date of each episode. When the intensity of an AE changes more than once a day, the maximum severity for the event should be recorded for that day. If the intensity changes over a number of days, these changes should be recorded separately (eg, as having distinct onset dates on one or more eCRF lines).

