To maintain consistency of reporting across clinical sites, findings of ARIA-E or ARIA-H on MRI are determined by the MRI Central Reader by radiologists with expertise in assessing for ARIA and other abnormalities on brain MRI. ARIA-E, ARIA-H, and other findings are documented on and reported to the sites with the BMW report (see [Section 6.3.12](#)). The BMW provided by the central reader after each MRI examination scores ARIA-E (parenchymal vasogenic edema, leptomeningeal/sulcal effusion) according to: extent, location, number of sites involved, radiographic severity (mild, mild+, moderate, moderate+, severe), and changes since prior MRI exams. ARIA-E findings typically resolve radiographically and will be noted as such on the BMW of follow-up MRI scans. The BMW also documents occurrence and characteristics (location, size, number) of ARIA-H (parenchymal microhemorrhages and leptomeningeal hemosiderosis and macrohemorrhages). Radiographic severity of ARIA-H findings (“mild”, “moderate”, “severe”) is defined as follows for the 3 categories of ARIA-H ([Table 7](#)):

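### Table 8 states no precedence between its grade rows and its seriousness rows, so for severe, serious, asymptomatic ARIA-H one row requires permanent discontinuation and another permits restart and up-titration

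*Protocol*

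**What the plan says.** Protocol Section 7.11.2 sends every participant with MRI evidence of ARIA to Table 8. Its rows use two classifications.

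- **Grade rows.** These use radiographic severity as defined in Table 7. ARIA-E of any grade, with or without symptoms, leads to suspension with possible restart. Mild or moderate ARIA-H leads to suspension if asymptomatic and to a permanent stop if symptomatic. Severe ARIA-H, whatever the symptoms, carries "Permanently discontinue treatment".
- **Seriousness rows.** Footnote c defines serious as "Meets criteria for a SAE". Serious symptomatic ARIA-E or ARIA-H leads to a permanent stop. Serious asymptomatic ARIA-E or ARIA-H leads to suspension until resolution or stabilization, after which "if participant dosing is restarted, they must receive the same dose they received immediately prior to the ARIA-E/ARIA-H findings". The same row then adds: "Participants who are undergoing dose titration when the ARIA occurs may continue up-titrating at the second post-resumption dose".

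A further row requires a permanent stop for "A second occurrence of ARIA-E after full resolution of a prior occurrence of ARIA-E".

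The two classifications have different sources. Section 7.11 states that "findings of ARIA-E or ARIA-H on MRI are determined by the MRI Central Reader", and the reader's worksheet supplies the grade. Seriousness follows Section 7.3, where "Important medical events that may not meet one of the above criteria could be considered a SAE by the Investigator". The note below Table 6 separates the two concepts: "a severe AE is not necessarily an SAE".

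**The concern.** A table that sorts the same event on two axes needs a rule for events that meet a row on each. Table 8 has none. Where the matching rows prescribe different actions, a site can follow one row correctly and do what another forbids.

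Dosing stops at once under every row, so the initial response is not in doubt. What is at stake is later re-exposure after a severe ARIA-H and, in the Titration Cohort, further dose escalation. ARIA is an identified risk of AL002 (Section 1.3), and its incidence and severity under titration form a primary endpoint.

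**Working it through.** No sample size, power or rate is involved. The check is to list the profiles and compare the rows.

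**Can the profile occur?** Table 7 grades ARIA-H as severe with 10 or more microhemorrhages, 2 or more areas of hemosiderosis, or 1 or more macrohemorrhages. Section 7.3 makes an event serious through inpatient hospitalization or as an important medical event, and neither requires symptoms. A single asymptomatic macrohemorrhage admitted for observation is therefore severe, serious and asymptomatic. That Table 8 has a serious asymptomatic row shows the protocol expects serious ARIA without symptoms.

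**Profiles.** Type (2) × grade (3) × symptoms (2) × seriousness (2) = 24 first-occurrence profiles. The 12 non-serious profiles meet only a grade row, so they cannot conflict. The 12 serious profiles meet one row of each kind:

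| Serious profiles | Number | Grade row | Seriousness row | Same action? |
|---|---|---|---|---|
| ARIA-E, any grade, asymptomatic | 3 | restart permitted | restart permitted | yes |
| ARIA-E, any grade, symptomatic | 3 | restart permitted | permanent stop | **no** |
| ARIA-H, mild or moderate, asymptomatic | 2 | restart permitted | restart permitted | yes |
| ARIA-H, mild or moderate, symptomatic | 2 | permanent stop | permanent stop | yes |
| ARIA-H, severe, asymptomatic | 1 | permanent stop | restart permitted | **no** |
| ARIA-H, severe, symptomatic | 1 | permanent stop | permanent stop | yes |

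Conflicts: 3 + 1 = 4 of 24.

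**Does any natural reading settle them?**

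1. *Grade rows govern.* Restart is permitted in 3 + 3 + 2 = 8 of 12 serious profiles. Seriousness then changes the action in 0 of 12, so both seriousness rows do nothing. That cannot be the intent.
2. *Seriousness rows govern, as exceptions.* Restart is permitted in 3 + 2 + 1 = 6 of 12. The three ARIA-E conflicts resolve to stop. But severe asymptomatic ARIA-H would stop when non-serious and could restart when serious, which is backwards. The serious asymptomatic row covers 3 + 2 + 1 = 6 profiles and agrees with the grade row in 5. Severe ARIA-H is the only profile it would change, and it would loosen it.
3. *The more specific row governs.* Neither row contains the other. The severe ARIA-H row also covers symptomatic and non-serious events; the serious asymptomatic row also covers ARIA-E and lower grades.
4. *The most restrictive row governs.* Restart is permitted in 3 + 2 = 5 of 12, with no conflicts and no reversals.

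The second-occurrence row was left out of the count. It reads as an exception and resolves to stop.

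**Is a rule stated elsewhere?** Protocol Sections 3.2.2, 4.3.1, 5.1, 6.3.12, 7.11.1 and 7.11.2 and Table 9 footnote g either point back to Table 8 or give general discretion. The precedence statement in SAP Section 1 concerns differences between protocol and SAP, not dosing rows.

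**The case against.** The strongest reply is that the two rows can both be obeyed. The severe ARIA-H row is unconditional. The serious asymptomatic row only regulates a restart if one happens and does not direct one. Permanent discontinuation complies with both, and since the lenient reading is perverse, a sensible investigator would reject it. That is fair as a prediction of behavior, but the protocol does not say it. A site that restarts has also followed a row as written. A reader who lets the seriousness row override grade for symptomatic ARIA-E must drop that principle for the asymptomatic row.

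A second reply points to the safeguards:

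- AESI reporting within 24 hours, with an automatic alert to the Medical Monitor (Section 7.2);
- SAE reporting within 24 hours (Section 7.7.1);
- an MRI before dose escalation (Section 6.3.12) and a check for incident ARIA before escalating (Section 1.3);
- an unblinded safety team (Section 5.1) and iDMC review (Section 12.1.1);
- the power to discontinue at any time (Section 4.3.1).

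These make unnoticed re-exposure unlikely, and that stands. None says which row applies. The 48-hour Medical Monitor contact in Section 7.11.2 is tied to symptoms or signs, so it misses this profile. Stabilization is no barrier either: under Section 7.11 it means no increase on a follow-up scan, which a persistent macrohemorrhage can meet.

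Three further points stand. The profile needs four conditions at once and is probably rare. The profile counts describe the table's logic, not risk. And Section 5.1 ties ARIA management to parent-study procedures that were not available, so sites may have a working rule that this protocol does not show.

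**Conclusion.** The concern holds. Table 8 gives incompatible permissions for one profile: severe, serious, asymptomatic ARIA-H. For three more, serious symptomatic ARIA-E at each grade, the stop action depends on an unstated reading. Confidence is high that the protocol and SAP state no rule; whether sites have one from another source is unknown.

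The number of participants affected cannot be estimated from the documents and is probably small. The three serious and severe parent-study cases described in Section 1.3 were symptomatic and in APOE e4/e4 participants, who are excluded here, so they are not evidence that this profile occurs.

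The effect on the titration comparison in SAP Section 7.4.8 is nil for the event that triggers Table 8, since that event is already counted for its own type. A later first event of the other type, such as ARIA-E after a restart following ARIA-H, could enter the corresponding CMH test. That effect is likely negligible.

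This should be corrected as a matter of participant safety. It does not threaten the analysis.

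**What to change.** Add one sentence to Table 8: *Where more than one row applies, the most restrictive action governs.* This gives each of the 24 profiles a single action and also covers the second-occurrence row. Optionally, limit the serious asymptomatic row to ARIA-E and mild or moderate ARIA-H, so that the rows agree on their face for that profile.

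The change can go out as a clarification letter or in the next amendment, with no new procedures or data. The cost is that a few participants who might have restarted would be permanently discontinued and, under Section 4.3.1, withdrawn from the study. Compared with letting grade rows govern, restart is lost in 8 − 5 = 3 serious profiles; compared with letting seriousness rows govern, in 6 − 5 = 1. In all four, some row of Table 8 already requires the stop.

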**7.12. [REDACTED]**

Ophthalmological examinations will be conducted at baseline and approximately every 4 months to monitor for [REDACTED]. These will include [REDACTED] examination, [REDACTED], [REDACTED], [REDACTED], and [REDACTED]. If evidence suggestive of [REDACTED] ( [REDACTED] ) is reported, the frequency of ophthalmologic examination should be increased to at least every 2 months until [REDACTED] is either ruled out or resolved.

**7.13. General Safety Monitoring**

**7.13.1. Special Situations**

Special situations are nonstandard medical conditions that provide valuable information about an investigational product. All special situations associated with an AE or SAE should be recorded in the EDC system in the AE eCRF. Special situations associated with SAEs must be reported within 24 hours of becoming aware. Special situations associated with AEs should be reported promptly.

Special situations are defined as below:

- **Overdose:** An overdose is any dose of study drug given to a participant or taken by a participant that exceeds the dose described in the protocol. There is no known treatment for AL002 overdose, and all participants should be monitored for AEs.
- **Off-label use:** Situations where a medicinal product is intentionally used for a medical purpose not in accordance with the authorized product information. It's the use of a pharmaceutical drug for an unapproved indication or in an unapproved age group, dosage or route of administration.
- **Misuse:** This refers to situations where the AL002 is intentionally and inappropriately used not in accordance with the prescribed or authorized dose, route of administration, and/or the indication(s) or within legal status of its supply.
- **Abuse:** This corresponds to the persistent or sporadic, intentional excessive use of AL002, which is accompanied by harmful physical or psychological effects.
- **Medication error:** A medication error is any dose of study drug given to a participant or taken by a participant that differs from the dose described in the protocol. Medication errors are not likely in the study, as the study drug is administered by IV infusion by trained personnel under the supervision of the Investigator or their designee.
- **Occupational exposure:** This corresponds to an AL002 for human use as a result of one's occupation.
- **Lack of efficacy/ effect:** Efficacy is the ability of a drug, biologic or device to produce desired therapeutic effect independent of potency (amount of the product needed for desired effect). Lack of efficacy/ effect, therefore, is the evidence of less than the expected effect of a product. There might be subpopulations that have a higher risk for lack of efficacy/ effect; in order to identify such cases, one needs to consider types of events that may be reported in such situations for the specific product and indications.

### **7.13.2. Pregnancy**

If applicable, pregnancy tests are to be performed at screening/baseline and/or at Week 49 and/or at EOS/ET (see Schedule of Assessments [Table 9](#)). Female participants must be instructed to discontinue all study drugs and inform the Investigator immediately if they become pregnant during the study.

The Investigator must report any pregnancy within 24 hours of becoming aware of it using the paper Pregnancy Report Form. Follow-up information documenting the pregnancy outcome should be reported on the paper Pregnancy Report Form. The site should email the Pregnancy Report Form to [[contact]](mailto:[contact]), according to the instructions provided in the Study Specific Regulatory Binder.

The participant must be immediately discontinued from study drug and/or PET imaging procedure. An uncomplicated pregnancy will not be considered an AE or SAE, but all pregnancies will be followed until a final outcome is known.

Pregnancies are captured if they occur in female participants or in the sexual partners of male participants from the time the participant is first exposed to the study drug or radiotracer until the final study visit.

Any congenital abnormalities associated with a pregnancy that occurred during study participation are considered SAEs. The outcome of any pregnancy and complete health information regarding the fetus will be recorded in the source documentation and reported to Pharmacovigilance.

Any SAE occurring in association with a pregnancy must be reported to Pharmacovigilance regardless of whether the events are considered related to study drug.

### **7.13.3. Breastfeeding**

All AEs that occur in infants following exposure to a study drug from breastmilk should be reported.

## 8. STATISTICAL METHODS AND ANALYSIS PLAN

All data for participants will be [REDACTED]. Analyses may [REDACTED] of this AL002-LTE study. Missing data will not be imputed, unless otherwise specified in the statistical analysis plan (SAP). The SAP will provide further details regarding the analysis sets and planned analysis methodologies to address all study objectives. Statistical analyses will be performed using [REDACTED].

Continuous data will be summarized using an [REDACTED], unless otherwise specified in the SAP. Categorical data will be summarized using [REDACTED], unless otherwise specified in the SAP.

Any changes to the data summaries and analyses outlined in this section will be documented in the SAP. Additional statistical analyses other than those described in this section may be performed if deemed appropriate. Any deviations from the analysis planned in the SAP will be justified and recorded in the final clinical study report (CSR).

Study endpoints are provided in [Section 2](#).

